right insula. Another group will receive TI-NDBS over the nucleus accumbens. Another group will receive TI-NDBS to the anterior cingulate cortex. We will not target these brain areas in any particular order. Prior to stimulation, subjects will be administered a questionnaire to assess their physical experiences and sensations using a 5-point Likert-scale. Subjects will also be given the Nicotine Dependence Syndrome Scale to assess baseline Nicotine Dependence. In addition, we will measure total real-time ad lib nicotine vapor inhalation during a 60 minute stimulation session. At the start of the stimulation, the current will increase slowly at a constant rate for 30 seconds until it reaches the appropriate intensity. At the end of the stimulation, the current will decrease slowly for 30 seconds until it reaches zero. Every ten minutes, we will ask subjects to self-report their level of craving on a Likert scale of 1-10. We will identify whether TI-NDBS to the insula or nucleus accumbens or cingulate is more effective stimulation at decreasing cravings. In the second stage of Phase 3, we will take the two most promising of the three brain regions and repeat the procedure of stage 1, but with a larger sample size. The third group will receive sham stimulation as a control. In both stages, immediately after stimulation, subjects will complete the stimulation experience scale and then again 30 minutes later. We will then follow up with subjects every day, up to three times per day, for a period of 1 week afterward using Ecological Momentary Assessment (EMA) via a smartphone app (LifeData) to monitor cigarette and/or vaping use and craving. The questions that will be used in the app are in a script attached (see EMA follow up questions). In Phases 1, 2, and 4 subjects are paid \$25/hr. In Phase 3, subjects are paid \$40/hr. In addition, in Phases 3 and 4, subjects are paid \$5/day for providing ecological momentary assessment data outside of the lab sessions, and \$10 bonus for completing 7 consecutive days of ecological momentary assessment (EMA). Payment will be made at the end of each day's lab session in cash, and for phase 3, by check after the EMA period ends.

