## **6.0 Statistical Analysis and Sample Size:**

In phase 1, we will assess tolerability with an initial cohort of 3 stimulation subjects. Our aim here is to identify any potential adverse effects, using two approaches. We will monitor the stimulation condition for clinically significant adverse effects such as seizures, prohibitive pain, etc, though we do not expect this based on all the literature from earlier studies.

In phase 2, we will conduct a pilot assessment to determine whether and how the stimulation immediately influences neural activity. As this is a within-subjects pilot design intended to estimate the effect size of neural activation, we will scan 10 subjects, comparing the neural activation in each subject during the stimulation period with neural activation in the same subject during the no-stimulation periods. We do not have a power analysis for this phase yet, because the whole point is to perform a pilot study in order to estimate the effect sizes. We anticipate that 10 subjects will be sufficient to estimate the effect sizes.

In phase 3, we will proceed in two parts. During the first pilot part, we will recruit 5 subjects in each of 3 groups, to identify which two of the three candidate brain regions seem most promising sites of stimulation to reduce nicotine craving and consumption. Once we identify the two more promising sites of stimulation, we will proceed to the second part. We do not have a power analysis for this part because again, we are looking to estimate the relative effect sizes for one stimulation site compared to another. For the second part, we will recruit 45 subjects who are heavy smokers into three groups of 15 each, then ask them to abstain from smoking for several hours prior to the session. The first group will receive TI-NDBS over the most promising site. The second group will receive TI-NDBS over the second most promising site. The third group will receive sham stimulation. We will measure total real-time ad lib nicotine vapor inhalation during a 60 minute stimulation session, and every ten minutes, we will ask subjects to

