self report their level of craving on a Likert scale of 0-10. We will identify whether TI-NDBS over the insula or nucleus accumbens is more effective than sham stimulation. We will then follow up with subjects 1 week afterward, using ecological momentary assessment (EMA) via smartphone apps (ilumivu.com) to assess cigarette use and craving. We expect to find that TI- NDBS reduces craving and cigarette consumption relative to sham. **Analysis and predictions:** We predict that TI-NDBS will outperform tDCS at reducing smoking and cigarette craving, which in turn will outperform sham stimulation. We will sum the total inhaled nicotine vapor over the 60 minute session and perform pairwise t-tests to determine if total drug intake is lower with one of the stimulation groups vs. sham. Also, we will average the self reported craving levels across each subject during the 60 minute session, and we will perform pairwise tests to determine if stimulation lowers self reported craving. During the 7 days following the stimulation session, we will give subjects the ilumivu app on their smartphones (or a loaner phone if needed), and we will notify them daily to request a self report of their level of craving and cigarette use in the preceding 24 hours. We will average these measures for each subject and perform an omnibus ANOVA (time point by group), followed by post-hoc pairwise tests to determine whether the stimulation led to longer lasting effects relative to sham. We will perform post-hoc tests for each of the 7 days to identify any differences in the duration of stimulation effects. For a power analysis, we do not yet know how many subjects will be necessary to achieve statistical power in the second part of phase 3, because we do not yet know what the effect sizes are. Nevertheless we anticipate that 15 subjects per group will provide a solid estimate of the effect sizes of stimulation relative to sham, so that we can write a grant to scale up the number of subjects based on a power analysis.

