In phase 4, we will compare TI-NDBS vs. conventional transcranial direct current stimulation for smoking reduction. To test this, we will recruit another 45 subjects who are heavy smokers into three groups of 15 each, then ask them to abstain from smoking. The first group will receive standard transcranial direct current anodal stimulation of the right DLPFC and cathodal stimulation of the left DLPFC (F3 and F4 in the 10/20 system). The second group will receive TI-NDBS to the most promising site as determined in phase 3. The third condition will be sham. We will assess craving levels every 10 minutes during the 60 minute stimulation period. We will repeat this for five consecutive days. We will then follow up with subjects 1 week after starting the tDCS, using ecological momentary assessment (EMA) via smartphone apps (ilumivu.com) to monitor cigarette use and craving. We will compare the sham vs. tDCS vs. TI-NDBS groups to identify differences in craving and relapse. **Analysis and predictions:** We expect to find that TI-NDBS leads to reduced craving and drug use relative to sham or tDCS. We will carry out the same statistical tests as in Study 1. As before, we do not yet know the effect sizes but will aim to estimate them based on the initial 45 subjects.

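### The 7-day EMA analysis averages for each subject and then runs a time-by-group ANOVA, with no rule for missed days; a mixed model on all reported days should replace it

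*Combined protocol and SAP*

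**What the plan says.** Section 6.0 (Phase 3, analysis and predictions) describes the follow-up data thus: "we will notify them daily to request a self report of their level of craving and cigarette use in the preceding 24 hours". The analysis is: "We will average these measures for each subject and perform an omnibus ANOVA (time point by group), followed by post-hoc pairwise tests". Its purpose is "to determine whether the stimulation led to longer lasting effects relative to sham", and it is followed by daily tests: "We will perform post-hoc tests for each of the 7 days to identify any differences in the duration of stimulation effects". The second stage of Phase 3 is small: "we will recruit 45 subjects who are heavy smokers into three groups of 15 each". For Phase 4 the same section says only: "We will carry out the same statistical tests as in Study 1". Study 1 is not defined there; the natural reading is Phase 3.

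Three other places bear on the point:

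- The Phase 3 description in section 3.0 gives a denser prompt schedule: "We will then follow up with subjects every day, up to three times per day, for a period of 1 week afterward". It also pays $5 a day for EMA data and, again in dollars, a "10 bonus for completing 7 consecutive days of ecological momentary assessment (EMA".
- The TI device section keeps EMA going when stimulation ends early. That is a different event from a subject ceasing to report.
- The contents list names minimising missing data as a topic for the statistical section. Sections 6.0 and 7.0 contain no minimum number of days, imputation rule, analysis set or sensitivity analysis.

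**The concern.** The bonus for an unbroken week suggests that full reporting is not taken for granted, yet the analysis is written as if every subject supplies all 7 days. The sentence also does not fix one analysis. A single mean per subject over the week cannot feed an ANOVA with time as a factor, and a mean within each day leaves the handling of absent days open. The choice could then be made after the data are seen.

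What rests on this step is the statement about lasting effects relative to sham and the daily tests of how long an effect persists. Section 6.0 also says that the Phase 3 effect sizes will be used to size a later grant application, so a distorted estimate would carry forward into that study.

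**Working it through.** **Inputs from the documents.** 15 subjects per arm and 7 daily reports (section 6.0). The 45 total is 3 × 15, which is right; no effect size, SD, power or drop-out rate stands behind it. Reporting rates, trends, SDs and stopping rates below are assumptions, because the documents give none.

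**1. Within-day average, then a conventional repeated-measures ANOVA.** Only subjects with all 7 days are used. With independent daily reporting probability p, the expected number is 15 × p^7:

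- p = 0.95: 0.698 × 15 = 10.5
- p = 0.90: 0.478 × 15 = 7.2
- p = 0.85: 0.321 × 15 = 4.8

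If missed days cluster in the same subjects, more remain at the same daily rate. As a scale only, take d = 0.71, the tDCS figure quoted in section 3.0. Approximate two-sided 5% power is Φ(d√(n/2) − 1.96). This gives 49% at n = 15, 37% at 10.5, 27% at 7.2 and 19% at 4.8.

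**2. Average over whichever days were reported.** A subject who stops after day k has mean day (k + 1)/2, against 4 for a full week. For k = 3 the mean day is 2. If craving rises by 0.5 points a day, the score is (4 − 2) × 0.5 = 1.0 point too low. If it falls by 0.25 a day, the score is (4 − 2) × 0.25 = 0.5 points too high. If it is flat, there is no shift.

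**3. Effect on the comparison when there is no true difference.** The simulation used two arms of 15, 7 days, craving starting at 4, between-subject SD 1.5, within-subject SD 1.0 and 1,500 runs per scenario. The daily stopping probability was 12% under stimulation and 2% under sham. If stopping is random, 0.88^6 = 46% and 0.98^6 = 89% complete the week. Entries are bias in points (negative favours stimulation) and the rate of a false benefit, nominally 2.5%. Simulation error on 2.5% is about √(0.025 × 0.975/1500) = 0.4 percentage points.

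| Craving trend per day | Who stops | Average of reported days | Completers only | Model on all reported days |
|---|---|---|---|---|
| +0.5 | at random | −0.40; 10.0% | +0.03; 2.5% | +0.01; 2.6% |
| +0.5 | high observed scores | −0.37; 10.2% | −0.54; 10.9% | −0.02; 2.5% |
| 0 | high observed scores | +0.06; 2.4% | −0.48; 10.6% | +0.02; 2.7% |
| −0.25 | at random | +0.20; 1.1% | −0.01; 1.9% | −0.01; 2.8% |

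With 8% stopping in both arms, every method was within 0.04 points of zero in every scenario. With no true effect the arms are interchangeable, so more stopping under sham reverses each sign. When stopping depends on the score that goes unreported, the model on all reported days keeps a bias of −0.05 to −0.09. The simulated model treated the covariance as known; a fitted one will do slightly less well.

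**The case against.** The strongest reply is that neither failure is written down. Section 3.0 allows as many as three prompts a day, so averaging for each subject may mean within a day. That keeps the time factor and fits the daily tests that follow. An ANOVA on all available subject-days is a further reading. This stands: the text is ambiguous, and the early-days problem belongs only to the over-days reading. It does not rescue the plan, because the within-day reading still needs a missed-day rule, and the conventional form of the named method discards incomplete subjects.

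A reader might infer that drop-out will make stimulation look beneficial, because people stop reporting once they smoke again. The documents do not support that. Section 6.0 asks Phase 3 subjects to abstain only for some hours before the session, not to quit. No smoking trend or stopping rate is given, and relapse is mentioned only for Phase 4. Falling craving, or more stopping under sham, turns the average's bias the other way.

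The payments and loaner phones should reduce missed days, but they are not an analysis rule. Section 5.0 does not list post-session EMA as an endpoint and the phases aim at effect-size estimation; this lowers the stakes without removing them. Finally, a mixed model alone cannot recover a worsening that no subject reports, so the sensitivity analysis is needed.

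**Conclusion.** The point holds as a weakness of the stated method. On one reading the ANOVA has no time factor and early stoppers are scored on early days; on the other, subjects with any missed day are lost. The loss could be large for arms of 15: 10.5, 7.2 or 4.8 remain under assumed independent reporting of 95, 90 or 85%, and more with clustering. Bias requires unequal stopping between arms. It also requires a trend over days (for the average) or stopping related to the score (for completers). Its direction cannot be predicted from the documents, and equal stopping gives none. All sizes rest on assumed inputs; what is certain is that no rule for missed days exists. The change should be made before the data are analysed.

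**What to change.** In section 6.0, Phase 3, replace the averaging and ANOVA with one linear mixed model for each EMA outcome, fitted to each subject's daily values. Average multiple prompts within a day only. Include group, day, group × day and a random subject effect. Use all allocated subjects with any reported day, including those who stopped stimulation early, and take the daily comparisons from the same model. Report the number reporting on each day by arm.

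Because the model assumes data are missing at random, add a sensitivity analysis that scores unreported days unfavourably: cigarettes at the subject's pre-study daily number, and craving by a stated upward shift. Record the pre-study number by subject ID at the lab visit. Screening cannot be relied on for it, since the Recruitment section says both that phone screens are kept in de-identified form and that nothing from screening is kept.

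Reconcile the EMA schedules so that a reported day is defined: daily for 7 days in section 6.0, as many as three times daily for a week in the Phase 3 description, and three times daily for two weeks in the New technology section. State the model again for Phase 4, where the EMA week is counted from the start of tDCS and overlaps the five stimulation days.

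The cost is protocol wording, one extra baseline item and a little more analysis work.

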conventional transcranial direct current stimulation for smoking reduction. To test this, we will recruit another group of subjects who are heavy smokers into three groups, then ask them to abstain from smoking. Prior to stimulation, subjects will be given the NDSS to determine baseline nicotine dependence. The first group will receive standard transcranial direct current anodal stimulation of the right DLPFC and cathodal stimulation of the left DLPFC (F3 and F4 in the 10/20 system). The second group will receive TI-NDBS to either the nucleus accumbens or anterior insula or anterior cingulate, depending on which is found to be more effective in Phase 3. The third condition will be sham. The strength of the stimulation and duration will be the same as in previous phases. Prior to stimulation, subjects will be administered a questionnaire to assess their physical experiences and sensations using a 5-point Likert-Scale. Immediately after stimulation, subjects will complete the stimulation experience scale, then complete the scale again 30 minutes later. In addition, we will assess craving levels every 10 minutes during the stimulation period. We will repeat this for five consecutive days. We will then follow up with subjects every day, up to three times per day, for 1 week after starting the tDCS, using EMA via a free smartphone app (ilumivu.com) to monitor cigarette use and craving. The questions that will be used in the app are in a script attached (see EMA follow up questions). We will compare the sham vs. tDCS vs. TI-NDBS groups to identify differences in craving and relapse. We expect to find that TI-NDBS leads to reduced craving and drug use relative to sham or tDCS. The procedure in this phase will not add anything new, except testing subjects with tDCS in addition to TI-NDBS and sham.

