For tDCS to the dorsolateral prefrontal cortex, we will place electrodes over F3 and F4. For TI-NDBS, we will use finite element methods ([simnibs.org](http://simnibs.org) or [sim4life](http://sim4life)) to determine where to place each of four electrodes (two pairs) in order to target the desired brain region. Each smoking subject will be allowed *ad lib* intake from our custom e-cigarette, which measures total inhaled vapor and thus nicotine intake (as we verified in Velez et al., 2015). As a measure of short-term neurostimulation effectiveness, we will compare total nicotine inhaled during stimulation for tDCS, TI-NDBS, and sham subjects. We will also ask for periodic self reports of craving during stimulation, i.e. “How much do you want to smoke?”, on a Likert scale of 0-10. We will compare self-reported craving across different stimulation conditions. For long-term assessment, we will use ecological momentary assessment, with the [Illumivu.com](http://Illumivu.com) system. Subjects will be prompted 3 times a day (morning, afternoon, and evening) between neurostimulation sessions and for the next two weeks following neurostimulation to report how many cigarettes they smoked in the preceding time period, and how much they are craving cigarettes at the moment. We will use this information to assess how strong the effect of stimulation is even after the stimulation session has ended. In the lab, we will measure recent smoking by measuring breath carbon monoxide (CO, Smokerlyzer PiCO).

[figure not shown]

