### **Recruitment:**

Participants are recruited by placing flyers around the community that ask for responses from “heavy smokers who are interested in research and are between the ages of 18-50 years”. Participants are also recruited via Craigslist using a post titled “Participants Needed for Psychology Study.” After calling or emailing the lab, interested participants complete a 5 minute phone screen to determine eligibility (e.g., smoking at least 15 cigarettes per day). These phone screens will be de-identified and retained to show eligibility to participate. Once in the laboratory participants also complete the nicotine dependence severity scale to quantify the severity of their nicotine dependence. [name] and Brown have successfully recruited populations of heavy smokers for fMRI studies in the past. Subjects who express interest by calling or emailing the lab will be contacted via telephone by the lab subject coordinator. They will be asked a series of screening questions to confirm that they meet the inclusion/exclusion requirements. This screening interview will be oral and no information will be recorded or retained, as it is for screening purposes only. If subjects meet the inclusion criteria, they will then be asked to provide a schedule of availability and placed on a list of interested subjects. They will be informed that they may or may not be offered a spot in our current study, depending on available timeslots and how many participants we will run in relation to how many interested respondents we have. As volunteers are needed for specific time slots, the research coordinator will contact them to schedule them, and the first subject that is available for the required session time will be scheduled. Interested participants who meet all screening criteria but who are not offered a slot in our current study will be informed that they have the option to be put on our contact list for future studies. Previously interested volunteers will be removed from the contact list immediately if they so request.

[figure not shown]

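### Phase 4 aims at smoking reduction and relapse, but plans no linked pre-stimulation cigarette count to adjust for and does not define relapse

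*Combined protocol and SAP*

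**What the plan says.** All references are to the combined protocol and SAP.

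- **Purpose.** Section 6.0 says of Phase 4: "we will compare TI-NDBS vs. conventional transcranial direct current stimulation for smoking reduction". The Phase 4 text in section 3.0 states the same aim. Both promise a three-group comparison of craving and relapse ("We will compare the sham vs. tDCS vs. TI-NDBS groups to identify differences in craving and relapse").
- **Abstinence.** In Phase 4, section 6.0 recruits "heavy smokers into three groups of 15 each, then ask them to abstain from smoking. The first group will receive standard transcranial" stimulation, with no start, length or check. The only stated length belongs to the second part of Phase 3: "ask them to abstain from smoking for several hours prior to the session".
- **Nicotine at sessions.** Section 3.0 (New technology) allows every smoking subject free use of the study e-cigarette and compares intake across tDCS, TI-NDBS and sham.
- **Cigarette counts.** EMA prompts subjects "to report how many cigarettes they smoked in the preceding time period". In Phase 3 this follows the session. In Phase 4 it runs for one week from the start of tDCS, while New technology has it run between sessions and for two weeks afterwards.
- **Baseline.** The Phase 4 text in section 3.0 names the NDSS. Breath CO is measured in the lab at unstated times. Under Recruitment, phone screens are to be kept without identifiers as proof of eligibility, yet the same paragraph says: "This screening interview will be oral and no information will be recorded or retained".
- **Endpoints and tests.** For Phase 4, section 5.0 lists craving, vapor inhalation and fMRI. Section 6.0 refers back to the tests of a Study 1, a label used nowhere else. Read as Phase 3, these are pairwise tests on session intake and craving, and a time-by-group ANOVA with post-hoc tests on EMA craving and cigarette use.

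**The concern.** A study of smoking reduction needs to know how much each subject smoked beforehand. Eligibility sets only a floor of three quarters of a pack a day, so a 15-a-day and a 40-a-day smoker can both enter and contribute to the arm mean with nothing to distinguish them. With 15 per arm, usual smoking may differ noticeably between arms, and the plan provides no variable with which to examine or adjust for it. Neither section 3.0 nor section 6.0 describes how Phase 4 subjects are allocated to groups, which makes such a variable more useful still.

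Relapse is a separate gap. Two analysts given the same Phase 4 data could not be expected to derive the same relapse variable. They would have to decide when abstinence began, whether vapor inhaled at a session counts, and when observation ends. Since Phase 4 is meant to supply effect sizes for later work, an imprecise smoking contrast and an undefined relapse contrast weaken its main product.

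**Working it through.** **1. Is there a figure to reproduce?** No. The Phase 4 size is 3 × 15 = 45, and section 6.0 says the effect sizes are unknown. The first check is therefore of what is measured and when.

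**2. Possible sources of a pre-stimulation smoking level.**
- EMA: starts with or after stimulation in every description. Section 6.0 gives a 24-hour look-back for Phase 3, so even a first report soon after a session would cover session time, not usual smoking.
- NDSS: described as a measure of dependence, not a count.
- Breath CO: reflects recent smoking, with no stated timing.
- Phone screen: two incompatible retention statements.
- Eligibility: 0.75 × 20 = 15 cigarettes a day (20 per pack assumed). This is a threshold, not an individual value.

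None is stated to give a usual cigarettes-per-day value under the subject ID, although Data Management keys the data by that ID.

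**3. What can still be computed.** The section 6.0 prediction is lower drug use relative to sham or tDCS. That is a difference between arms and needs no baseline. Change from a subject's own level does need one.

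**4. Precision without a baseline.** The standard error of a difference between two arms is SD × √(2/15) = 0.365 × SD. The documents give no SD, so assume 5 to 10 cigarettes a day:
- SD 5: 1.83, 95% range ±3.6.
- SD 10: 3.65, 95% range ±7.2.

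This is ordinary sampling error, already included in the t-test's standard error.

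**5. Gain from adjustment.** With baseline-to-follow-up correlation r (assumed), the residual variance is 1 − r² and the standard error shrinks by √(1 − r²):
- r = 0.5: 1 − 0.25 = 0.75, so 25% of variance is removed. SE 1.58 (SD 5) to 3.16 (SD 10).
- r = 0.8: 1 − 0.64 = 0.36, so 64% is removed. SE 1.10 to 2.19.

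**6. The same gain as power.** This is an illustration only, using the d = 0.71 for cigarette consumption after five days of tDCS quoted at the start of section 3.0. With two-sided α 0.05, no multiplicity adjustment and a normal approximation, power = Φ(0.71 / (√(1 − r²) × √(2/15)) − 1.96):
- no baseline: Φ(1.944 − 1.96) = 49% (exact t: 47%)
- r = 0.5: 61%
- r = 0.7: 78%
- r = 0.8: 90%

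**7. Relapse.** Event: not defined. Abstinence period: not stated for Phase 4. Endpoint in section 5.0: absent. Test in section 6.0: none for a binary or time-to-event outcome. Window: one week from the start of five daily sessions leaves about 7 − 5 = 2 days after the last one, against 14 days under New technology.

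**The case against.** The best defence is that the planned contrast is between arms and Phase 4 exists to estimate effects. Chance imbalance in usual smoking is then part of the standard error and biases nothing, and the SDs and correlations above are assumed. All of that stands. It limits the point to precision and to the meaning of reduction, and makes no case that the comparison is invalid. The NDSS, and breath CO if taken before stimulation, could also serve as covariates. They could, but the plan does not say so, and neither is the outcome measured earlier.

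Four stronger readings are tempting, and the documents do not support them:
- *That subjects make no quit attempt.* Phase 4 asks them to abstain, without a time limit. Whether that means quitting or a pre-session fast cannot be told from the text. A flyer seeking people interested in research says nothing about intent to quit.
- *That nearly everyone relapses in every arm.* This follows only if the Phase 3 limit of several hours also governs Phase 4. If it does, relapse would hardly differ between arms, but the text does not settle it.
- *That neither outcome can be measured.* EMA counts and session intake support a comparison between arms. With a definition, EMA counts and breath CO might support relapse too.
- *That the phone screen cannot be linked.* Removing identifiers does not rule out a study ID, and the two statements conflict, so its status is unknown.

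The EMA script is an attachment not in the public document. The point therefore rests on what the protocol text states.

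**Conclusion.** The point holds as one of missing baseline information and an undefined outcome. As written, Phase 4 can report only an unadjusted post-stimulation difference in smoking between arms of 15. It cannot report reduction from a subject's own level or adjust for usual smoking. Relapse is promised but cannot be derived reproducibly. It is undefined rather than unmeasurable.

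The size is a loss of precision that is almost free to avoid: 25% to 64% of outcome variance at an assumed correlation of 0.5 to 0.8. At the quoted d = 0.71, this corresponds to power of 61% to 90% instead of 49%. A reader might take the standard error of 1.8 to 3.7 cigarettes a day as bias. It is ordinary sampling error under assumed SDs. The change should be made before Phases 3 and 4 enrol, because the baseline cannot be collected prospectively afterwards.

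**What to change.** 1. At consent in Phases 3 and 4, record usual cigarettes per day under the subject ID. Ask for the usual level rather than the last day's, since subjects may already be abstaining.
2. In section 6.0, replace the unadjusted EMA cigarette-use ANOVA with an ANCOVA or mixed model (group, time, their interaction) that includes this value as a covariate. Name Phase 3 explicitly where the text says Study 1.
3. In section 5.0, make adjusted cigarettes per day the Phase 4 smoking outcome.
4. In sections 3.0 and 6.0, either drop relapse or keep it with a stated event, abstinence period, window and test, and say how session vapor is treated.
5. Reconcile the abstinence wording across the Phase 3 and Phase 4 texts in sections 3.0 and 6.0, the EMA duration (Phase 4 texts against New technology), and the two retention statements under Recruitment.

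The cost is one question, one model term and some wording. Starting the EMA prompts a few days before the first session would give a better baseline, but is optional: it adds those days at the existing $5 a day and requires consent and app set-up before the session day.
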